8.3 Exploratory endpoints

- Change in frequency of hot flashes from Pre-dose (Day -1) as assessed by skin conductance
- Change from Baseline in frequency of moderate to severe hot flashes, hot flash average severity and hot flash severity score as measured by twice daily paper diary throughout study
- Change in frequency of hot flashes as measured by continuous day time diary from Day -1 pre-dose to Day 7 and Day 14
- Change from Baseline in night-time-awakenings (NTA) secondary to hot flashes as measured by paper diary
- Change in LH AUC_{0-8 hours} on Day-1 versus Day 1 and Day 7
- To explore the relationship between plasma concentrations and placebo-corrected change from baseline QTcF and QTcB values using concentration effect modeling, depending on the results observed

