3.5 Exploratory Endpoints

The exploratory endpoints are as follows:

- Change in frequency of hot flashes from predose (Day -1) as assessed by skin conductance
- Change from baseline in frequency of moderate to severe hot flashes, hot flash average severity, and hot flash severity score, as measured by twice daily diary throughout the study
- Change from baseline in frequency of hot flashes as measured by continuous day time diary from Day -1 predose to Day 7 and to Day 14
- Change from baseline in night time awakenings (NTA) secondary to hot flashes as measured by twice daily diary
- Change in luteinizing hormone (LH) AUC₀₋₈ hours on Day-1 versus Day 1 and Day 7

- To explore the relationship between plasma concentrations and placebo-corrected, change from baseline QTcF and QTcB values using concentration effect modeling, depending on the results observed.

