5 CHANGES IN THE CONDUCT OF THE STUDY OR PLANNED ANALYSIS

The conduct of the study and planned analyses are consistent with the study protocol (Version 4.0, dated 13 December 2016). The exposure response analysis on QTcB will not perform since this correction method is not regarded as appropriate ; per the Q&A E14, question 1.5 (available at http://www.ich.org/fileadmin/Public_Web_Site/ICH_Products/Guidelines/Efficacy/E14/E14_Q_As_R3_Step4.pdf).

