8.10.2 Continuous Hot Flash Diary

8.10.2.1 Frequency of Hot Flashes

Frequency by day

Daily (24-hour) frequency of hot flashes for Day Y for the continuous hot flash diary will be equal to the number of hot flashes recorded on Day Y (day period + night period)

The daily frequency of mild, moderate, severe, moderate/severe, and total hot flashes as measured by continuous day-time diary will be summarized for each day. The mean (+SE) in frequency of mild, moderate, severe, moderate/severe, and total hot flashes will be displayed graphically by day. The change from Day -1 will also be summarized.

Average daily frequency by week

The average daily frequency of hot flashes for Week 1 will be equal to the average of the daily frequency of hot flashes from Day 1 to Day 7, inclusive.

The Week 1 average frequency of mild, moderate, severe, moderate to severe, and total hot flashes will be summarized by treatment.

Statistical analysis

The analysis will test the treatment difference of daily frequency of moderate/severe hot flashes from Day -1 to Day 7 and Day 14.

The analysis will be based on a linear mixed-effects model with the change from Day -1 as a dependent variable, treatment, day and treatment-by-day interaction as fixed effects, subject as a random effect, and the number of moderate/severe hot flashes at Day -1 and the interaction with day as covariates. Subjects dosed with placebo will be analyzed as a pooled group. An unstructured covariance matrix will be specified for the repeated measures at postdose timepoints for each subject. From this analysis, the LS mean and 2-sided 90 % CIs will be calculated for the contrast “NT-814 versus placebo” at each treatment and each postdose day, separately.

Following is the SAS code for reference:

```
proc mixed data=dataset ;  
class TRT <50 mg NT-814, 100 mg NT-814, 150 mg NT-814, etc..., placebo> DAY <7,14> USUBJID;  
model CHG = TRT DAY TRT*DAY BSL BSL*DAY / s ddfm=kr;  
random USUBJID;  
repeated DAY / type=un subject=USUBJID;  
lsmeans TRT*DAY / cl diff alpha=0.1;  
run;
```

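### The continuous-diary endpoint covers all hot flashes, but the SAP's only model-based comparison with placebo for that diary is of moderate/severe flashes

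*SAP*

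**What the plan says.** Protocol 8.3 lists two diary frequency endpoints next to each other. The twice-daily diary endpoint carries a severity limit: "Change from Baseline in frequency of moderate to severe hot flashes, hot flash average severity and hot flash severity score". The continuous-diary endpoint does not: "Change in frequency of hot flashes as measured by continuous day time diary from Day -1 pre-dose to Day 7 and Day 14". The protocol synopsis draws the same distinction, and SAP 3.5 repeats the unrestricted continuous-diary endpoint: "Change from baseline in frequency of hot flashes as measured by continuous day time diary from Day -1 predose to Day 7", and on to Day 14.

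SAP 8.10.2.1 then sets out the analysis of that diary. The descriptive part is broad: "The daily frequency of mild, moderate, severe, moderate/severe, and total hot flashes as measured by continuous day-time diary" is summarised for each day and plotted, with change from Day -1 and a Week 1 average. SAP 8.1 makes these summaries by treatment, with placebo pooled across cohorts. The inferential part is narrow: "The analysis will test the treatment difference of daily frequency of moderate/severe hot flashes from Day -1 to Day 7 and Day 14". The baseline terms match it: "the number of moderate/severe hot flashes at Day -1 and the interaction with day as covariates". The output, Table 14.2.2.1.3, is titled for moderate/severe flashes.

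SAP section 5 states: "The conduct of the study and planned analyses are consistent with the study protocol". The one departure it names is dropping the QTcB exposure-response analysis.

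**The concern.** The quantity listed as the endpoint and the quantity modelled are not the same. A moderate/severe count responds to two different effects: flashes that stop, and flashes that still occur but are rated mild. A total count responds only to the first. The planned contrast therefore cannot by itself say whether NT-814 reduces how often flashes occur, which is what the continuous-diary endpoint asks.

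No other model fills the gap. The twice-daily frequency model in SAP 8.10.1.1 is also for moderate/severe flashes, so no SAP model compares total self-reported flash frequency with placebo.

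There is a second consequence. SAP 8.10.3 applies the 8.10.2.1 model to the skin-conductance data, where the count is every device-detected flash, with no severity attached. The diary model and the device model then have the same form and use the same days, but count different events.

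**Working it through.** The plan states no figure on this point, so there is nothing to reproduce. The check is a comparison of text, followed by simple arithmetic.

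**Endpoint against analysis, continuous diary**

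| Item | Where | Severity scope |
|---|---|---|
| Listed endpoint | Protocol synopsis, Protocol 8.3, SAP 3.5 | none stated |
| Daily and Week 1 summaries, by treatment | SAP 8.10.2.1 with 8.1 | mild, moderate, severe, moderate/severe, total |
| Model outcome and baseline covariate | SAP 8.10.2.1 | moderate/severe |
| Contrast and 90% CI | SAP 8.10.2.1, Table 14.2.2.1.3 | moderate/severe |
| Same model applied to the device | SAP 8.10.3 | all detected flashes |
| Declared departure | SAP section 5 | QTcB only |

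**What each contrast measures**

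Let M be the moderate/severe flashes per day at baseline, f the fraction that NT-814 turns into mild flashes, and r the fraction that it stops. Assume that placebo does not change and that mild flashes are otherwise unaffected. Then:

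- moderate/severe change = -(f + r) × M
- mild change = +f × M
- total change = -r × M

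The two contrasts agree only when f = 0. Their difference is f × M.

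**Numbers**

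M is taken from the entry criterion of 7 to 20 moderate to severe flashes per day (Protocol 7.2). That criterion is a screening average from the twice-daily diary, used here as a stand-in for the Day -1 continuous-diary count. The documents give no value for f or r, so both are assumed.

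Pure shift to mild (r = 0):

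| M | f = 0.1 | f = 0.3 | f = 0.5 | Total change |
|---|---|---|---|---|
| 7 | -0.7 | -2.1 | -3.5 | 0 |
| 10 | -1.0 | -3.0 | -5.0 | 0 |
| 20 | -2.0 | -6.0 | -10.0 | 0 |

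Half shift and half removal (f = r = 0.15, M = 10): moderate/severe change = -0.30 × 10 = -3.0; total change = -0.15 × 10 = -1.5.

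Pure removal (f = 0, r = 0.30, M = 10): both changes are -3.0.

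A proportional fall common to both arms scales these figures down. With an assumed 15% fall, the pure-shift contrast at M = 10 and f = 0.3 becomes -0.30 × 10 × 0.85 = -2.55, and the total contrast stays at 0.

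I give no probabilities of a significant result, because the documents state no variance for flash counts.

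**The case against.** The case for leaving the plan alone is substantial, and most of it stands.

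- **Disclosure.** A reader might infer that a shift from moderate to mild would be reported as fewer flashes. The documents do not support that. The inferential table names moderate/severe in its title, and the planned summaries would show mild flashes rising and the total unchanged.
- **Comparison with placebo.** A reader might infer that the listed endpoint is never set against placebo. That also goes too far. Total flashes and their change from Day -1 are tabulated for each dose and for pooled placebo. What is missing is a model-based contrast with an interval.
- **Status.** Protocol 11.3.4 describes efficacy analysis as mainly descriptive, and Protocol 11 pre-specifies no primary hypothesis test. The protocol promises no test of this endpoint, so the consistency statement in SAP section 5 is incomplete rather than clearly false.
- **Intent.** It is tempting to say that the two diary definitions differ deliberately. Neither document says so. Protocol 8.4 itself states the eligibility threshold for moderate to severe flashes and then repeats it without the severity qualifier, so loose wording is a real possibility.
- **Severity elsewhere.** SAP 8.10.1.2 and 8.10.1.3 model average severity and severity score from the twice-daily diary against placebo. A move to milder flashes should appear in average severity.
- **Objective and subjective measures.** The exploratory objective calls for both kinds of measure but plans no formal comparison of them.

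These points limit the consequence but do not remove the mismatch. As written, the endpoint has no severity limit, the modelled variable has one, and the SAP does not record the difference.

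**Conclusion.** The point holds in a limited form. The continuous-diary endpoint is total hot flash frequency, its only placebo contrast and 90% CI are for moderate/severe flashes, and section 5 is silent on this. The planned contrast differs from the one for the listed endpoint by f × M. For an assumed f of 0.3, that is 2.1 to 6.0 flashes per day across the entry range; if flashes are only removed, it is zero. The direction follows from arithmetic alone. The size is illustrative and rests on an assumed f, no other change in mild flashes, and a stable placebo group.

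The practical loss is a missing formal estimate. Total frequency remains visible in the descriptive tables. For an exploratory endpoint, the priority is low to moderate.

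**What to change.** In SAP 8.10.2.1, also fit the stated mixed model to change from Day -1 in total (mild + moderate + severe) frequency, with the Day -1 total and its interaction with day as covariates. Report its contrasts and 90% CIs in Table 14.2.2.1.3 beside the moderate/severe results, and widen the table title to cover both. The moderate/severe model can stay as it is and need not be demoted. Add a line to section 5 stating that the continuous-diary endpoint has no severity limit and that both counts are modelled.

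The cost is one more run of a model already specified, a short wording change and one more unadjusted exploratory comparison. No new data are needed. If the sponsor in fact meant moderate/severe flashes, restating the endpoint in SAP 3.5 and recording the change in section 5 would resolve the inconsistency, but total self-reported frequency would still have no interval estimate.

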8.4 Study design

This is a multi-center, double-blind, randomized, placebo-controlled multiple ascending dose trial in post-menopausal women with vasomotor symptoms.

Subjects will be recruited into a maximum of 5 sequentially dosed cohorts; Cohort 1 (50 mg NT-814), Cohort 2 (100 mg NT-814), Cohort 3 (150 mg NT-814) and, if needed, 2 further cohorts up to 400mg NT-814. See [Figure 1](#) for study design schematic.

For each cohort, subjects will enter a 4 week screening period to determine eligibility. Twenty eligible subjects will be randomized per cohort (15 active and 5 placebo).

During the screening period each subject will be required to complete twice daily paper diaries. Eligible subjects will demonstrate, at the Baseline visit, an average 24-hour moderate to severe hot flash frequency ≥ 7 and ≤ 20 based upon the average daily frequency of all available readings (at least 4 days) in the final week of screening (Week -1). If at the Baseline visit subjects have an average 24-hour hot flash frequency < 7 /day or > 20 /day they will be discontinued from the study. In addition, subjects that have a change of $\geq 50\%$ in average 24-hour hot flash frequency between the first and second week of the screening period (Week -2 and Week -1 respectively) will be excluded. Subjects will also be provided with the continuous daily diary during screening and instructed to start completing this on the morning of Day -1 after waking, prior to admission to the clinic, and to continue to complete this throughout Day -1.

It may be necessary to extend a patient's screening period beyond 28 days (with the approval of the sponsor) when a subject is held over from one cohort to the next because the original cohort into which they would have been enrolled is complete. If this occurs, the following safety procedures must be repeated such that the most recent evaluation occurs within 28 days of the rescheduled randomization:

- Biochemistry and hematology
- Vital signs
- 12-lead ECG
- Physical examination

If the subject has completed (or partially completed) the screening twice daily Hot Flash Diary this must still be repeated and a new diary started on the new planned Day -15 and completed for the 2 weeks up to Day -2. Eligibility will be assessed on the repeated diary, not the initial one. If the subject had not started completing their screening diary at the time screening was put on hold, they will start this screening diary on the re-scheduled Day -15.

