8.10.1 Twice Daily Hot Flash Paper Diaries

8.10.1.1 Frequency of Hot Flashes

Frequency by day

Daily (24-hour) frequency of hot flashes for Day Y will be equal to the number of hot flashes recorded on Day Y (day time hot flushes recorded in the evening + night time hot flushes recorded the following morning).

The daily frequency of mild, moderate, severe, moderate/severe, and total hot flashes will be summarized for each day. The mean (\pm SE) frequency of mild, moderate, severe, moderate/severe (moderate and severe combined), and total hot flashes will be displayed graphically by day (Day -8 onwards).

Average daily frequency by week

The average daily frequency of hot flashes for each of Week -1, Week 1, and Week 2 will be equal to the average of the daily frequency of hot flashes from Day -8 to Day -2 inclusive, from Day 1 to Day 7 inclusive, and from Day 8 to Day 14 inclusive, respectively.

The average daily frequency by week and the change from Week -1 (for Week 1 and Week 2) of mild, moderate, severe, moderate/severe, and total hot flashes will be summarized descriptively by treatment.

Statistical analysis

The analysis will test the treatment difference of change in the average daily frequency of moderate/severe hot flashes from Week -1 to each of Week 1 and Week 2.

The analysis will be based on a linear mixed-effects model with the change from Week -1 as a dependent variable, treatment, week, treatment-by-week interaction as fixed effects, subject as a random effect, and baseline (frequency of moderate/severe hot flashes at Week -1) and baseline-by-week interaction as covariates. Subjects dosed with placebo will be analyzed as a pooled group. An unstructured covariance matrix will be specified for the repeated measures at postdose timepoints for each subject. From this analysis, the least-squares (LS) mean and 2-sided 90% CIs will be calculated for the contrast “NT-814 versus placebo” for each treatment and each postdose week, separately.

Following is the SAS code for reference:

```
proc mixed data=dataset ;  
class TRT <50 mg NT-814, 100 mg NT-814, 150 mg NT-814, etc... , placebo> WEEK <1,2> USUBJID;  
model CHG = TRT WEEK TRT*WEEK BSL BSL*WEEK / s ddfm=kr;  
random USUBJID;  
repeated WEEK / type=un subject=USUBJID;  
lsmeans TRT*WEEK / cl diff alpha=0.1;  
run;
```

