8.10.2.2 Night Time Awakenings

8.10.2.2.1 Night Time Awakenings Secondary to Hot Flashes

Night time awakenings secondary to hot flashes for Day Y = the sum of the number of moderate and severe night time hot flashes recorded on the continuous diary (as these are defined as resulting in a night time awakening) .

Frequency by day

The NTA secondary to hot flashes will be summarized for each day and displayed graphically by day. The change from Day -1 will also be summarized.

Average daily frequency by week

The average daily NTA secondary to hot flashes for Week 1 will be equal to the average of the NTA from Day 1 to Day 7. The average daily NTA secondary to hot flashes for Week 1 will be summarized by treatment.

The same statistical analyses for the daily scores as described in section 8.10.2.1 will be done based on the change from Day -1 NTA.

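### The continuous-diary models adjust only for the single Day -1 value; adding the Week -1 average already held from the twice daily diary would make the exploratory comparisons with placebo somewhat more precise

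*SAP*

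**What the plan says.** For the continuous diary, SAP 8.10.2.1 states: "The analysis will be based on a linear mixed-effects model with the change from Day -1 as a dependent variable". The only baseline terms are "the number of moderate/severe hot flashes at Day -1 and the interaction with day as covariates", and the reference code agrees: "model CHG = TRT DAY TRT*DAY BSL BSL*DAY / s ddfm=kr". BSL is the one-day continuous-diary count. For awakenings secondary to hot flashes, SAP 8.10.2.2.1 refers back: "The same statistical analyses for the daily scores as described in section 8.10.2.1 will be done based on the change from Day -1 NTA".

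For the twice daily diary, SAP 8.10.1.1 derives "The average daily frequency of hot flashes for each of Week -1, Week 1, and Week 2", with Week -1 running "from Day -8 to Day -2 inclusive". That model does adjust for the week: "baseline (frequency of moderate/severe hot flashes at Week -1) and baseline-by-week interaction as covariates". SAP 8.10.1.4.1 derives the matching Week -1 average for awakenings secondary to hot flashes.

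The Week -1 frequency is also an entry criterion. Protocol 8.4 has it "based upon the average daily frequency of all available readings (at least 4 days) in the final week of screening (Week -1"), and SAP 8.2 likewise needs 4 complete days for any weekly score.

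**The concern.** Hot flash counts vary from day to day, so a single day carries only part of the information about a woman's usual level. Day -1 is also the admission day, with monitors being fitted and serial ECG and LH sampling. The documents themselves want at least 4 days before they accept a weekly frequency. Whatever usual-level variation the Day -1 count misses stays in the residual and widens the 90% CI for each dose against placebo on Day 7 and Day 14. With 15 women per dose, that precision is worth having if it needs no new data.

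**Working it through.** **No plan figure to reproduce.** The only power statement (Protocol 11.1, SAP 8.12) concerns plasma AUC. No SD, correlation or precision target is given for any hot flash measure, so every correlation below is an assumption.

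**Inputs from the documents.** Two-sided alpha is 0.1 (SAP 8.10). There are 15 active and 5 placebo women per cohort, with placebo pooled (SAP 4.1, 8.10.2.1). That gives 20 placebo women with the four cohorts named in the PK SAP (section 3), or 25 with five. Week -1 rests on m = 4 to 7 days.

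**Assumed quantities.** rho is the correlation between one woman's counts on two days. r is the correlation between the two diaries' underlying levels. a is a factor (1 or 0.8) by which the baseline-to-post-dose covariance is weakened.

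**Step 1: change or count makes no difference.** With the Day -1 value as covariate and a separate slope for each day, subtracting Day -1 from the outcome only shifts that slope by -1. Treatment contrasts and residual variance are the same, so the question is what the baseline covariates explain.

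**Step 2: formulas.** Set the single-day variance to 1 and take each outcome day as an ANCOVA.
- Day -1 only: residual variance = 1 - (a·rho)².
- Day -1 and Week -1: residual variance = 1 - c'S⁻¹c, where c = (a·rho, a·r·rho) and S has diagonal 1 and rho + (1 - rho)/m, off-diagonal r·rho.
- CI width ratio = square root of (second / first). The contrast SE is the residual SD × √(1/15 + 1/20) = 0.342 (0.327 with 25 placebo women), which cancels in the ratio.

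**Step 3: one case in full.** Take rho = 0.5, r = 0.8, m = 7, a = 1.
- Day -1 only: 1 - 0.25 = 0.750.
- Week -1 variance: 0.5 + 0.5/7 = 0.5714. Determinant of S: 0.5714 - 0.16 = 0.4114.
- c'S⁻¹c = (0.25 × 0.5714 - 2 × 0.5 × 0.4 × 0.4 + 0.16)/0.4114 = 0.1429/0.4114 = 0.347.
- Both: 1 - 0.347 = 0.653. Ratio √(0.653/0.750) = 0.933, so the CI is about 7% shorter.

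**Step 4: the range (m = 7, a = 1).** Residual variance, Day -1 only → both, with the CI width ratio in brackets:

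| r | rho 0.3 | rho 0.5 | rho 0.7 |
|---|---|---|---|
| 1.0 | 0.910 → 0.768 (0.919) | 0.750 → 0.556 (0.861) | 0.510 → 0.336 (0.811) |
| 0.9 | 0.910 → 0.801 (0.938) | 0.750 → 0.613 (0.904) | 0.510 → 0.407 (0.893) |
| 0.8 | 0.910 → 0.828 (0.954) | 0.750 → 0.653 (0.933) | 0.510 → 0.444 (0.933) |
| 0.6 | 0.910 → 0.867 (0.976) | 0.750 → 0.703 (0.968) | 0.510 → 0.482 (0.972) |

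**Step 5: features that shrink the gain.**
- Four days instead of seven: at r = 0.8 the ratio is 0.962, 0.941 and 0.938 for rho 0.3, 0.5 and 0.7.
- Weaker baseline-to-post-dose link (a = 0.8, m = 7, r = 0.8): 0.972, 0.962 and 0.969. The weakest setting tried (a = 0.8, r = 0.6, rho = 0.8) gives 0.992.
- Day-to-day autocorrelation of 0.5, simulated at r = 1: variance cuts of 9.5%, 17.3% and 25.0%, so ratios √0.905 = 0.951, √0.827 = 0.909 and √0.750 = 0.866.
- Entry limits (Week -1 mean 7 to 20, change below 50%), simulated: 0.85-0.92 at r = 1, 0.92-0.95 at r = 0.9 and 0.97-0.98 at r = 0.7.

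**Step 6: cost in degrees of freedom.** With 80 women and one extra covariate per outcome day, the expected CI width grows by about 0.7%. That cancels the gain only near the weakest setting.

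**Step 7: power scale.** For 15 v 20 at alpha 0.1 (noncentral t, 33 df), take an effect with 70% power under Day -1 only. With both covariates (m = 7, a = 1), power is 74-75% at r = 0.8 and about 72% at r = 0.6.

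**Step 8: replacing Day -1 instead.** With Week -1 alone and a = 1, the ratio to Day -1 alone is 0.80-0.92 at r = 1 (m = 7) but 1.01-1.42 at r = 0.6, over rho 0.3 to 0.8.

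**The case against.** The strongest objection is that Week -1 is not a repeat of the same measurement. SAP 4.8.1 describes two different diaries. Week -1 comes from twice daily entries made before admission. Day -1, Day 7 and Day 14 in this model come from flashes logged as they occur, largely in the clinic. A lasting clinic or instrument effect would be shared by Day -1 and the outcome days but not by Week -1. The entry limits also narrow the spread of the Week -1 average. All of this stands. A reader might infer a CI 8% to 19% shorter (the r = 1 row above); the documents do not support that, because it assumes perfect agreement between the diaries and ignores the entry limits.

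The second objection is that nothing is broken. Adjusting the change from Day -1 for Day -1 on the same instrument is standard and matches the endpoint definition. The efficacy analyses are exploratory and carry no precision target, and the twice daily diary model already uses Week -1. This also stands, and it limits the importance of the point. It does not remove the gain, since the SAP commits to a 90% CI for each dose and day.

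The third is a side effect. SAP 8.10.3 applies the 8.10.2.1 model to skin conductance, so a careless edit would put a diary covariate into the device analysis. That is correct, and the fix has to deal with it.

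**Conclusion.** The point holds as an optional efficiency improvement. The two continuous-diary models leave out a multi-day pre-randomization average that is already to hand. Adding it reduced the residual variance in every setting tried. The size rests wholly on assumed correlations: a 90% CI roughly 1% to 15% shorter before the small degree-of-freedom cost. The upper end is the r = 1 result with the entry limits applied. The 5-7% at r = 0.8 and 2-3% at r = 0.6 assume seven complete days, no attenuation and no truncation. No calculation is specific to awakenings; the daily-count figures are carried over to them.

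Two stronger readings should be resisted. A reader might infer that the planned comparison is biased or invalid. It is not: Day -1 precedes dosing, treatment is randomized, and the omission costs only precision. A reader might also infer that Week -1 is the better baseline and should displace Day -1. Step 8 shows this could lose precision if the diaries agree poorly, and the documents give no information on their agreement.

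**What to change.** In SAP 8.10.2.1, keep the Day -1 count and add the Week -1 average daily moderate/severe frequency from the twice daily diary, with its interaction with day. The code line becomes `model CHG = TRT DAY TRT*DAY BSL BSL*DAY WKM1 WKM1*DAY / s ddfm=kr;`. In 8.10.2.2.1, add the Week -1 average of awakenings secondary to hot flashes (from 8.10.1.4.1) in the same way. The dependent variable, the contrasts and the intervals reported stay as they are.

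State that the addition applies to the diary models only, and say in 8.10.3 that the skin conductance model keeps its Day -1 covariate alone. The table list also has a statistical analysis of continuous-diary total awakenings (Table 14.2.2.3.3), which the text does not describe; say whether the Week -1 term applies there.

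The cost is a wording change, one merged variable per model and two model degrees of freedom, with no new data. Very few women should lack the covariate, because entry already requires at least 4 days of Week -1 diary. The change should be made before the blind is broken, when Protocol 11.3 requires the SAP to be final.
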